**e. Sample size calculation.**

The present study aims to determine the number of participants needed to determine the effect of a dance therapy program administered to patients with severe mental disorders. Preliminary studies cited in the literature have determined that dance therapy has the potential to influence aspects such as emotional state, memory or executive functions, being observable through neuropsychological and EEG tests. The working hypothesis is that dance therapy will produce a statistical effect, involving cognitive improvement, observable in subsequent assessments of neuropsychological test scores and electroencephalographic activity patterns in those diagnosed with severe mental disorder. Therefore, in this study we tried to determine two independent sample means.

The calculation of statistical power was performed by means of two independent ("unilateral") means, based on the variance of a control group and the reference group with a minimum of 13 study subjects, in accordance with systematic reviews of previous scientific studies such as Jiménez et al. (2019). The probability of the degree of statistical significance was based on values of  $p<0.05$  with the statistical tests applied, with a 95% confidence interval.

The sample was calculated using GRANMO software (Marrugat et al., 1998). In this line, in order to estimate the probability that the observed phenomenon is true and not due to chance with the calculated sample size, the alpha risk was determined. Specifically, an  $\alpha=0.05$  was chosen, which assumes a 95% confidence level. To control for the potential of the analysis, a power of 80% was selected, with a beta of 0.2. To define the ratio between two groups (control and experimental), the ratio between group 1 and group 2 was indicated, the ratio being a value of 1, as these are two groups with equal sample sizes. In addition, as we are calculating on the basis of means, the standard deviation has been included. Since we do not have a pilot project with previous data before and after the dance therapy program proposed in the current project, the following process was used to find the standard deviation:

1. Review of previous literature on mental health and dance therapy; 2. Screening of dance therapy manuscripts with patients presenting with a pathology encompassed

within severe mental disorder (see Ren & Xia, 2013); 3. Selection of the manuscript by Röhricht & Priebe (2006) to estimate the standard deviation of the sample needed for the dance therapy intervention group. Specifically, this manuscript details a controlled trial with body-oriented psychological therapy similar to that performed in dance therapy with a group of patients framed within severe mental disorder. For standard deviation we took the means before and after dance therapy. Specifically, we have selected the values of the measures obtained in the negative symptoms of the PANSS scale, since they are one of the mental health values mainly suggested for statistical significance post-intervention with dance therapy in severe mental disorder. In this case, since in our study we also consider a follow-up of the success of the intervention after the implementation of the program, we have selected the mean of the negative symptoms of the PANSS before the intervention with dance therapy (23.4), the mean of these symptoms after finishing a program similar to the dance therapy program proposed in this project, also of 20 sessions for 10 weeks (18.9) and, as in our proposal, the mean of a follow-up after -after several months- the intervention program with dance therapy (18.2). Considering these means as a data set, they were entered into the Calcuvio software ([www.calcuvio.com](http://www.calcuvio.com)) which runs as a statistical calculator returning mean, sample and population standard deviation values. Specifically, the standard deviation of the set of numbers was found according to the study segment using the following equation:

$$\sigma = \sqrt{\frac{\sum_{i=1}^n (x_i - \bar{x})^2}{n-1}} = \sqrt{\frac{(x_1 - \bar{x})^2 + (x_2 - \bar{x})^2 + \dots + (x_n - \bar{x})^2}{n-1}}$$

A sample standard deviation of 2.822 was obtained for the intervention group; 4. Selection of the manuscript by Chao & Xiaolin (2022) to estimate the sample standard deviation needed for the control group without dance therapy. Specifically, this manuscript details an evaluation of the application of the effect of dance therapy in the rehabilitation process of patients whose pathology is framed within severe mental disorder. For the standard deviation, the means of the sample of participants in the control group of the study were taken before and after the parallel development of the

intervention program with dance therapy with the experimental group. In particular, to find the standard deviation of our control group sample with severe mental disorder, the mean values of the negative symptoms of the PANSS scale were chosen again (as they show significant statistical differences in scores between the control group and the experimental group in the manuscript of Chao & Xiaolin, 2022). In this case, the control group presented a mean of 14.98 on negative symptoms before the parallel start of the dance therapy intervention program, and a mean of 11.32 after the conclusion of the dance therapy intervention stage in the experimental group. Considering these means, we proceeded to calculate the sample standard deviation with the same procedure and software previously used to find the standard deviation of the intervention group in the previous point. Here we obtained a value for the sample standard deviation of our control group of 2.588.

In addition to the above, as the starting hypothesis is that the dance therapy program will improve emotional management and increase cognitive performance, it can be assumed that the minimum response to the program will be double (2).

After performing the mathematical calculation, accepting an alpha risk of 0.05 and a beta risk of 0.2 in a unilateral contrast, 28 participants in the intervention group are required to detect a difference equal to or greater than 2,822 units, as well as 28 participants in the control group to detect a difference equal to or greater than 2,588 units.

In addition, an expected rate or proportion of loss to follow-up of 10% ( $10/100=0.1$ ) due to experimental errors, drop-out, etc., has been estimated in the intervention group, with participants engaged in the dance therapy intervention. On the other hand, a loss-to-follow-up rate or proportion of 25% ( $25/100=0.25$ ) has been estimated in the control group with participants not engaged in the dance therapy intervention. This expected increase in losses in the control group is based on the hypothesis that the patient who does not receive the intervention may not be as involved in the experiment or, eventually, debut with pathological manifestations associated with their medical condition leading to absenteeism or indisposition during the data collection stage.

Therefore, considering the respective loss to follow-up rates in both the experimental group and the control group, the final (n) for each group would be as follows: experimental group with an  $N=28$ , after expected loss to follow-up of 10% out of 28

equals 2.8 participants, would be left with a final (n) of 26 participants; control group with an N=28, after expected loss to follow-up of 25% out of 28 equals 7, would be left with a final (n) of 21 participants.

In conclusion, for this project we need 47 participants (21 participants for the control group and 26 participants for the experimental group receiving intervention with dance therapy). It is also worth mentioning that each participant will sign a pre-test consent to participate in data acquisition and, if applicable, intervention in the dance therapy program as part of the research project. These consents will inform them of the aims of the study, risks if applicable, and answer any questions or queries they may have.

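### The sample size uses the spread of published group means over time as a patient standard deviation, and for a secondary outcome, so the stated 80% power has no valid basis

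*Combined protocol and SAP*

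**What the plan says.** Section 2.e (Sample size calculation) describes a one-sided comparison of two independent means with alpha 0.05, where "a power of 80% was selected, with a beta of 0.2" and the allocation ratio is 1. It explains why it turned to the literature: "Since we do not have a pilot project with previous data". It then states how the SDs were obtained: "For standard deviation we took the means before and after dance therapy". The calculation itself is described as follows: "Considering these means as a data set, they were entered into the Calcuvio software".

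- **Intervention group.** Three mean PANSS negative-symptom scores from one published trial (23.4 before, 18.9 after, 18.2 at follow-up) give an SD of 2.822.
- **Control group.** Two means from a different study are used: "the control group presented a mean of 14.98 on negative symptoms before" the programme, "and a mean of 11.32 after the conclusion of the dance therapy intervention stage". These give an SD of 2.588.

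PANSS negative symptoms were chosen "since they are one of the mental health values mainly suggested for statistical significance post-intervention". The minimum response is set at double (2), with no unit. The section concludes that 28 per group are required, to detect 2,822 units in the intervention group and 2,588 in the control group. It then deducts losses of 10% and 25% to arrive at 26 and 21.

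The section on study variables makes cognition, especially memory and executive functions, the main variable and places PANSS among the secondary ones. The main objective is framed on BACS, MoCA and EEG.

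**The concern.** The SD in a two-means formula stands for the variation between patients within a group. The spread of one group's mean across visits contains no information about that. A control group whose mean did not change would yield an SD of zero and a required sample of zero, however different its patients were.

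The outcome is also not the one on which the trial will be judged. Nothing in the plan gives a between-patient SD for any outcome, or a target difference for any cognitive score.

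The 80% is the plan's only formal justification for its size. If the cognitive comparison is not significant, readers will weigh that result against a power and a detectable difference that were never established.

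**Working it through.** **1. The plan's SDs reproduce.** Sample SD with divisor n − 1:

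- Intervention: the mean of 23.4, 18.9 and 18.2 is 20.167. The squared deviations sum to 15.927, and √(15.927/2) = 2.822.
- Control: with two values the SD is their difference divided by √2, so (14.98 − 11.32)/√2 = 3.66/√2 = 2.588. This is the mean change, rescaled.

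**2. The plan's 28 and 28 reproduce.** Using n per group = 2(1.645 + 0.842)² SD²/d², with d = 2 and each group's own SD:

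| Group | SD | n | Rounded | After allowance for losses |
|---|---|---|---|---|
| Intervention | 2.822 | 24.6 | 25 | 25/0.90 = 27.8 → 28 |
| Control | 2.588 | 20.7 | 21 | 21/0.75 = 28 |

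This is a reconstruction. The text presents 28 as the number required and deducts losses afterwards, whereas the arithmetic fits only if 28 already includes them.

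**3. The printed detectable differences do not give 28.** With d equal to the SD, n = 2(1.645 + 0.842)² = 12.4, so 13 per group before losses (14 with the exact t calculation). Of the values printed, only d = 2 leads to 28.

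**4. The SD depends on which visits are counted.** The intervention figure uses three time points and the control figure two. With before and after only, the intervention SD is (23.4 − 18.9)/√2 = 4.5/√2 = 3.182. Then n = 31.3, rounded to 32, and 32/0.90 = 35.6, so 36 (35 if rounding is left until after the loss step). The requirement rises from 28 to 35 or 36 with no change in any patient's variability.

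**5. Power on the plan's own inputs.** With 26 and 21 evaluable, the standard error is √(2.822²/26 + 2.588²/21) = 0.791, and 2/0.791 = 2.53. One-sided power at 0.05 is 80.1% (noncentral t, 45 df) or 81.2% (normal approximation).

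**6. What can be said without an SD.** For a standardised difference δ, the noncentrality is δ√(n₁n₂/(n₁ + n₂)) with n₁ + n₂ − 2 df. The second row applies the plan's losses to the 26 and 21 that the Design and Workplan sections assign: 26 × 0.90 = 23.4 and 21 × 0.75 = 15.75, so 23 and 16. The Mann-Whitney columns divide δ by √0.955, its efficiency for normal data.

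| Evaluable | t, one-sided | t, two-sided | Mann-Whitney, one-sided | Mann-Whitney, two-sided |
|---|---|---|---|---|
| 26/21 | 0.74 SD | 0.84 SD | 0.76 SD | 0.86 SD |
| 23/16 | 0.82 SD | 0.94 SD | 0.84 SD | 0.96 SD |

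At 26/21 (t test), an assumed true effect of 0.5 SD has 51% power one-sided and 39% two-sided. An assumed 0.8 SD has 85% and 76%.

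**7. Illustration for PANSS negative symptoms only.** With d = 2, one-sided, 26/21, and assumed common between-patient SDs of 2, 2.7, 4 and 5, power is 96%, 80%, 51% and 38%. These SDs are not in the documents, and the list cannot be read across to BACS or MoCA.

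**The case against.** The authors had no pilot data, looked for published trials in similar patients, and gave reasons both for choosing PANSS negative symptoms and for including the follow-up mean. They also cite a systematic review for a minimum of 13 study subjects. On their inputs the calculation works, and actual power could turn out to be adequate. The fault does not bias the group comparison or raise the type I error rate.

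All of that is fair, and it limits the claim: no direction of error is shown. But a lack of pilot data explains using the literature, not substituting means for a patient SD. The reasons given bear on the choice of outcome and visits, not on the measure of spread. The minimum of 13 supplies no SD.

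Two cautions on the alternative figures also stand. They assume one outcome at one time point, near-normal data and no adjustment for multiple tests, while the plan has several BACS subtests, a bounded MoCA and three visits. And the statistical analysis section plans Mann-Whitney tests and mixed models, not a t test, so the figure quoted must match the test actually used.

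**Conclusion.** The concern holds and must be fixed. Both SDs are demonstrably the spread of group means over time for a secondary outcome. The 80% power is therefore unsupported for PANSS negative symptoms, and the main cognitive outcomes have no power calculation at all. True power is unknown rather than shown to be low.

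That the SDs are of the wrong kind needs no outside assumption: it follows from the plan's description and is confirmed by exact reproduction of 2.822 and 2.588. The reading of how 28 arose (d = 2, losses already included) is inferred from the arithmetic. The power figures for particular effects or SDs rest on the assumed values stated with them.

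**What to change.** In section 2.e, delete the SDs derived from means and withdraw the 80% claim for 2,822 and 2,588 units. Then do one of the following.

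- **(a) Recompute.** Use a between-patient SD of the chosen cognitive score, or of its change, with a justified difference, and give the source of both.
- **(b) State the scale-free figure.** For example: *With 26 and 21 evaluable participants, a two-sample t comparison at alpha 0.05 has 80% power for a difference of 0.74 SD (one-sided) [or 0.84 SD, two-sided]; with 23 and 16 evaluable, 0.82 SD [or 0.94 SD]. SD is the between-patient SD of the quantity compared (final score, change, or baseline-adjusted score).* If Mann-Whitney is the main test, name it instead and use about 0.76 [0.86] SD for 26/21 and 0.84 [0.96] SD for 23/16, for normal data.

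Keep only the side that will be used. Section 2.e is one-sided and the statistical analysis section names no side, so state the same one there.

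The cost is a rewording of section 2.e and one phrase in the statistical analysis section. Option (b) needs no extra patients, visits or tests, but the stated figure is less favourable. Option (a) may change the required number in either direction.

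### The sample size section describes the target effect as a 'double' response and as 2.822/2.588 units, but its 28 per group reproduces with a 2-point difference that is never stated or sourced

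*Combined protocol and SAP*

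**What the plan says.** Study methodology, section 2.e (Sample size calculation), sets up a comparison of two independent means, "accepting an alpha risk of 0.05 and a beta risk of 0.2 in a unilateral contrast". The allocation is equal, "the ratio being a value of 1, as these are two groups with equal sample sizes".

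The effect to be detected appears twice, in different terms:

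- As a multiple: "it can be assumed that the minimum response to the program will be double (2". The only support is the starting hypothesis that the programme helps. No scale, unit or reference is attached.
- As a detectable difference: 28 participants in the intervention group for 2.822 units and 28 in the control group for 2.588 units.

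The same section takes PANSS negative-symptom means from two published studies, and uses them only to obtain SDs. For dance therapy it takes the "mean of the negative symptoms of the PANSS before the intervention with dance therapy (23.4"), then 18.9 at the end of the programme and 18.2 at follow-up. For control, "the control group presented a mean of 14.98 on negative symptoms" at the start and "a mean of 11.32 after the conclusion of the dance therapy intervention stage". The SD of the first three means is 2.822; the SD of the last two is 2.588.

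**The concern.** A two-means calculation needs one absolute between-arm difference, in points of a named scale. A ratio of 2 and a difference of 2 points are different assumptions, and the text argues for the first while printing a bare 2. The figures then given as detectable differences are dispersion measures, one per arm, whereas a between-arm contrast has a single target difference.

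The effect assumption drives the sample size. As written, a reader cannot learn what effect the 80% power refers to. Someone who takes either printed description literally will believe the trial is sized for something it was not sized for.

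**Working it through.** **Inputs, all from section 2.e:** one-sided alpha 0.05 (z = 1.645); power 80% (z = 0.842); ratio 1; SDs 2.822 and 2.588; losses 10% (intervention) and 25% (control). (1.645 + 0.842)² = 6.183.

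**Formula:** n per group = 2 × 6.183 × SD² / d², rounded up, then divided by (1 − loss) and rounded up.

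**1. Reproducing the plan's 28 and 28, with d = 2 points**

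- SD 2.822: 12.366 × 7.964 / 4 = 24.6, so 25; 25 / 0.90 = 27.8, so **28**.
- SD 2.588: 12.366 × 6.698 / 4 = 20.7, so 21; 21 / 0.75 = **28**.

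Both stated figures come out, with the losses already inside them.

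**2. Do the printed descriptions give 28?**

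| Difference entered | Before losses (intervention, control) | After losses |
|---|---|---|
| 2 points, one-sided | 25, 21 | 28, 28 |
| Equal to the SD (2.822; 2.588), one-sided | 13, 13 | 15, 18 |
| 3.66 points (control fall doubled), one-sided | 8, 7 | 9, 10 |
| 2 points, two-sided | 32, 27 | 36, 36 |

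The third row takes doubling literally: the control fall is 14.98 − 11.32 = 3.66, twice that is 7.32, and the between-arm difference is 7.32 − 3.66 = 3.66.

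**3. Do the source means support doubling?**

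- Dance-arm fall to the end of the programme: 23.4 − 18.9 = 4.5. Control-arm fall: 3.66. Ratio 4.5 / 3.66 = 1.23; difference 0.84.
- Dance-arm fall to follow-up: 23.4 − 18.2 = 5.2. Against the same control fall, ratio 1.42 and difference 1.54. No control follow-up mean is given, so this pairing is looser.

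Neither ratio is near 2.

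**4. Illustrative power, taking the plan's SDs at face value**

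SE at 26 and 21 = √(2.822²/26 + 2.588²/21) = 0.791. Power = 1 − Φ(1.645 − d/SE).

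- d = 2: 81%.
- d = 1.54: 62%.
- d = 0.84: 28%.

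If 26 and 21 are the numbers assigned, as the Design and Workplan sections read, and the stated losses then occur, 23.4 and 15.75 remain. The SE is 0.875 and power at 2 points is 74%.

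**The case against.** Several points on the other side have force.

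*The documents do not show what was entered in the software.* True: the 2-point entry is inferred. Nor is it the only value that can yield 28. With both SDs together and no loss inflation, n = 6.183 × (7.964 + 6.698) / d² equals 28 at d of about 1.8. But 1.8 appears nowhere in the plan, whereas 2 does, and with the plan's own loss rates it returns 28 in both arms. Under either route the printed descriptions remain wrong.

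*The plan never offered the source means as an effect.* This stands, and it limits the point. A reader might infer that the sources suggest an effect of 0.84 points and that the trial therefore has about 28% power instead of 80%. The documents do not support that. The 0.84 subtracts a change in one study's control arm from a change in another study's dance arm, with baselines of 23.4 and 14.98. Both sources had their own comparison groups, and the between-arm results of those comparisons are not given in the plan. The means show only that doubling was not derived from these figures.

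*The SDs cannot carry a power figure.* This also stands. They are SDs of two or three group means, not between-patient SDs. If the patient SD were 4 to 7 (an assumption; the documents give none), power at 2 points with 26 and 21 would be about 52% down to 25%. So neither 28% nor 81% measures the trial's real power.

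*The figures concern PANSS negative symptoms.* The Study variables section makes PANSS secondary, and the main objective is memory and executive function. Nothing here shows how informative a negative cognitive result would be.

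**Conclusion.** The point holds as a misstatement of the target effect. The section describes the effect as a doubling and as 2.822/2.588 units; the stated 28 per group matches neither, and reproduces with 2 points on PANSS negative symptoms. The gap is material: the printed descriptions correspond to 7 to 8 or 13 per arm before losses, against 25 and 21 with 2 points. The 2-point value has no stated source, and the cross-study ratio of about 1.2 lends doubling no support.

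This rests on the inference that 2 was entered as points, one-sided, once per SD, with losses added. It does not establish what the true effect is, what the trial's real power is, or that enrolment is too small.

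**What to change.** In section 2.e:

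1. Delete the 'double (2)' justification and the sentence giving 2.822 and 2.588 units as detectable differences.
2. State that the calculation assumed an absolute between-arm difference of 2 points on PANSS negative symptoms, a secondary variable, with a one-sided test. The sponsor should confirm this against the software entry. Give the source of the 2 points, or say that there is none.
3. State that the 80% power applies only to that difference and to the SDs used, and is not power for the cognitive main objective.
4. If a sensitivity line is added, show power at smaller differences with 26 and 21: about 28% at 0.84, 62% at 1.54 and 81% at 2 points, or about 74% at 2 points if the stated losses fall on 26 and 21. Label these as illustrative, because the SDs are SDs of group means and the smaller differences are cross-study contrasts.

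The cost is protocol wording and a less favourable power statement. Correcting the statement requires no change to enrolment.

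### The sample-size result prints the two standard deviations (2.822 and 2.588) as detectable differences, one per arm, although 28 per arm fits a single difference of 2

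*Combined protocol and SAP*

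**What the plan says.** Section 2.e plans a comparison of two independent means. Its settings are "a power of 80% was selected, with a beta of 0.2" and an allocation described as "the ratio being a value of 1, as these are two groups with equal sample sizes".

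The SDs come from published mean scores on the PANSS negative scale. For the intervention arm: "A sample standard deviation of 2.822 was obtained for the intervention group". For the control arm: "Here we obtained a value for the sample standard deviation of our control group of 2.588".

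The section then assumes a minimum response described as a doubling, with the figure 2 in brackets and no unit or outcome.

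The result is given for a one-sided test at alpha 0.05 and 80% power. For the intervention arm it reads: "28 participants in the intervention group are required to detect a difference equal to or greater than 2,822 units". The statement for the other arm has the same form with its own figure: "28 participants in the control group to detect a difference equal to or greater than 2,588 units". The comma is a decimal comma. The text turns to losses (10% intervention, 25% control) only after this, subtracts them from 28, and arrives at 26 and 21, total 47. Study Methodology, 1. Design randomises a minimum of 47 (26 and 21), and the Workplan tests 47 at baseline.

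**The concern.** The same two numbers serve first as standard deviations and then as differences to be detected. No between-arm difference of 2.822 or 2.588 is derived or justified anywhere. The result also assigns one difference to each arm, which has no meaning for a two-sample comparison.

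This is the result line of the protocol's only sample-size justification. A reader uses it to learn what the trial was sized to find, and here it does not follow from the inputs. Because the real target is hidden, a reader also cannot see that 28 per arm appears to include the loss allowance already. That bears on how 47 should be read.

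**Working it through.** **Inputs, all from section 2.e.** One-sided alpha 0.05 (z = 1.645); power 80% (z = 0.842); ratio 1; SDs 2.822 and 2.588; losses 10% and 25%; the bracketed figure 2.

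**SDs.** The sample SD of 23.4, 18.9 and 18.2 is 2.822. The sample SD of 14.98 and 11.32 is 2.588. Both printed values are reproduced.

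**Formula.** Per arm, n = 2 × (1.645 + 0.842)² × SD² / d², where (1.645 + 0.842)² is 6.183 with unrounded z values. Enrolled number = n / (1 − loss).

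**Reproducing 28 and 28, with d = 2.**
- Intervention: 2 × 6.183 × 2.822² / 4 = 24.6, so 25; 25/0.90 = 27.8, so 28.
- Control: 2 × 6.183 × 2.588² / 4 = 20.7, so 21; 21/0.75 = 28.

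Both arms match. This uses the normal approximation. The t distribution gives 25.3 and 21.4, so 26 and 22 before losses.

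**Taking the printed differences at face value.**
- With d equal to the SD in either arm, n = 2 × 6.183 = 12.4, so 13 (13.1, so 14, by the t distribution). After losses, 13 becomes 15 at 10% and 18 at 25%.
- Across separate and pooled SDs (pooled 2.708), d = 2.822 or 2.588 gives 11 to 15 per arm one-sided, at most 20 after losses. Two-sided it gives 14 to 19, at most 26 after losses. None gives 28.
- For 28 evaluable per arm to be what 80% power requires, the SD would have to be about 4.25 (d = 2.822) or 3.89 (d = 2.588). Neither is in the documents.
- Two two-sided runs with d = 2 and no losses come close (27 with SD 2.588, 29 with the pooled SD), but the plan specifies a one-sided test.

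**Power and detectable difference, accepting the SDs.** SE = √(2.822²/n₁ + 2.588²/n₂).

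| Evaluable (intervention/control) | Power at 2.0 | Power at 2.588 | Power at 2.822 | Difference detectable with 80% power |
|---|---|---|---|---|
| 28/28 (SE 0.724) | 86.8% | 97.3% | 98.8% | 1.80 |
| 26/21 (SE 0.791) | 81.2% | 94.8% | 97.3% | 1.97 |

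The 25 and 21 from the reproduction give 80.5% power for a difference of 2, so that pair is coherent.

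**If 47 is the enrolled number.** 26 × 0.90 = 23.4 and 21 × 0.75 = 15.75. With 23 and 15 evaluable, SE = 0.890 and power for a difference of 2 is about 73%.

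**The case against.** Several points on the other side stand.

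- **The error runs in the safe direction.** On the plan's inputs, power at 2.822 and 2.588 is well above 80%, both at 28/28 and at 26/21. A reader might infer that the trial is too small for what it claims, or that 28 is wrong. The documents do not support either: 28 is recoverable, and the printed differences are larger than those detectable with 80% power.
- **The target of 2 is inferred.** The text gives it no unit or outcome, and a doubling reads literally as a ratio. Exact reproduction in both arms is good evidence of what was entered, not proof. A reader might state as fact that the trial was designed for 2 points; the documents do not say so.
- **The outcome is secondary.** The inputs are PANSS negative scores, whereas the main objective is cognition and EEG. A reader might infer that a null main result would be judged against the wrong threshold. It would not be judged in PANSS units at all.
- **The SDs are spreads of three and two group means over time.** Every detectable difference above is conditional on them. Their validity and the choice of PANSS are separate issues, and resolving either would replace this sentence.

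None of this rescues the sentence. It calls SDs differences and gives one to each arm, and this is wrong whether or not 2 was the target and whether or not the SDs are sound.

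**Conclusion.** Wrong as written, as a reporting error of moderate weight. The printed differences are the two SDs. If 2 was the target, they exceed it by 41% (2.822/2) and 29% (2.588/2). A difference equal to the SD would need 13 or 14 evaluable per arm. The 28 and 28 fit a difference of 2 with each arm's SD and loss rate.

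The mislabelling itself rests on no assumption. The target of 2 is an inference for the sponsor to confirm, and 1.80 and 1.97 hold only if the SDs are accepted. N need not change for this correction. A related inconsistency remains: 28 and 28 appear to include losses already, yet losses are subtracted again to reach 47, which is then used as the number randomised.

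**What to change.** In section 2.e, delete 2,822 and 2,588 units as detectable differences and label both values as SDs only. Confirm the intended between-arm difference, and state it once with its outcome and unit. If it is 2 points on the PANSS negative score, wording could be: *for a between-arm difference of 2 points, one-sided alpha 0.05 and 80% power, 25 evaluable participants are needed in the intervention arm (SD 2.822) and 21 in the control arm (SD 2.588), that is 28 and 28 enrolled after losses of 10% and 25%.* Do not write 25 per arm: 25/0.75 = 33.3, so control would need 34.

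Add the difference detectable with 80% power at the number actually analysed (1.80 at 28/28, 1.97 at 26/21, if the SDs are kept).

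Reconcile this with the end of section 2.e, the Design section and the Workplan by saying whether 47 is the enrolled or the evaluable number. If 47 is enrolled, restate the power (about 73% for a difference of 2 after the stated losses).

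Correcting the sentence costs wording only. The reconciliation may cost more: enrolling 28 and 28 means 56 participants, nine more than 47, whereas keeping 47 as the enrolled number means reporting the lower power.

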## **STUDY METHODOLOGY**

### **1. Design**

A single-centre prospective randomised controlled trial will be conducted with a minimum of 47 patients with severe mental disorder (SMD) who will be randomly assigned into two groups, 1 intervention group receiving dance therapy (n=26) and 1 control group who will not receive any intervention or added treatment apart from continuing with their usual treatment (pharmacological), but will not receive intervention with dance therapy (n=21).

In summary, the groups are:

- Experimental group (n=26): people with SMD receiving dance therapy.
- Control group (n=21): people with SMD who do not receive the dance therapy intervention but do receive their usual pharmacological treatment.

Tests will be administered before the start of the study and at the end of the study, as well as 3 months after the end of the study in order to compare the results between groups.

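### Expected losses are subtracted from the required 28 per arm and the remaining 47 are randomised, so the plan does not reach its own stated 80% power

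*Combined protocol and SAP*

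**What the plan says.** Section 2.e sets a one-sided alpha of 0.05, 80% power and an allocation ratio described as "the ratio being a value of 1, as these are two groups with equal sample sizes". The SDs are 2.822 (intervention) and 2.588 (control), each obtained from published group means of PANSS negative symptoms: "Considering these means as a data set, they were entered into the Calcuvio software". For the effect, the plan says that "it can be assumed that the minimum response to the program will be double (2" in brackets, with no unit and no statement of what was entered in the calculator. The result is that "28 participants in the intervention group are required to detect a difference equal to or greater than 2,822 units", and likewise 28 in the control group for 2,588 units (decimal commas).

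Expected losses are 10% in the intervention arm and 25% in the control arm. The section subtracts them from 28. For the intervention arm, the loss "equals 2.8 participants, would be left with a final (n) of 26 participants"; for control, "after expected loss to follow-up of 25% out of 28 equals 7, would be left with a final (n) of 21 participants". It ends: "In conclusion, for this project we need 47 participants".

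The Design section then plans "a minimum of 47 patients with severe mental disorder (SMD) who will be randomly assigned into two groups", 26 and 21. The Workplan gives the baseline tests to the same 47 and names the same arm sizes.

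**The concern.** An allowance for loss should raise the number randomised above the number needed for analysis. Here it lowers it. Because 47 is the number that starts the trial, the 10% and 25% losses fall on 26 and 21, and the control arm, against which hypotheses H1a and H1b are tested, shrinks most. The stated 80% is the plan's only justification for its size.

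Other figures in the same section also disagree: the detectable differences repeat the SDs, the subtraction for the intervention arm does not give 26, and 26:21 is not a ratio of 1.

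**Working it through.** **Inputs (section 2.e).** One-sided alpha 0.05 (z = 1.645); power 80% (z = 0.842); ratio 1; SDs 2.822 and 2.588; losses 10% and 25%. *Assumption:* the bracketed 2 is the difference entered, d = 2 units.

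**1. The SDs.** The sample SD of 23.4, 18.9 and 18.2 is 2.822. The sample SD of 14.98 and 11.32 is 2.588. Both reproduce.

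**2. The two 28s.** n per arm = 2 × (1.645 + 0.842)² × SD² / d².

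| Arm | n from formula | Rounded up | Inflated for loss |
|---|---|---|---|
| Intervention, SD 2.822 | 24.62 | 25 | 25 / 0.90 = 27.8, so 28 |
| Control, SD 2.588 | 20.70 | 21 | 21 / 0.75 = 28 |

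Two SDs with two loss rates both give 28. Other readings tried do not:

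- one-sided, d = 2, no loss: 25 and 21
- two-sided, d = 2, no loss: 32 and 27
- two-sided, d = 2, with loss: 36 and 36
- d equal to the SD, no loss: 13 and 13 one-sided, 16 and 16 two-sided

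So 28 most likely already contains the allowance for loss, and the plan then removed it.

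**3. The subtraction.** 28 − 2.8 = 25.2, which the plan gives as 26; 28 − 7 = 21. Total 26 + 21 = 47.

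**4. Completers.**

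- 47 randomised: 26 × 0.90 = 23.4 and 21 × 0.75 = 15.75, about 23/16 (39).
- 56 randomised: 28 × 0.90 = 25.2 and 28 × 0.75 = 21, about 25/21 (46).

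**5. One-sided power at d = 2.** Normal method: Φ(d / (SD × √(1/n₁ + 1/n₂)) − 1.645). For 23/16, √(1/23 + 1/16) = 0.3255. With SD 2.822, 2 / (2.822 × 0.3255) = 2.177, and Φ(2.177 − 1.645) = 0.703. The t method uses the noncentral t distribution with n₁ + n₂ − 2 degrees of freedom. The last column gives each arm its own SD.

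| Completers | SD 2.822, t / normal | SD 2.588, t / normal | Both SDs, t / normal |
|---|---|---|---|
| 25/21 (56 randomised) | 0.762 / 0.773 | 0.823 / 0.833 | 0.79 / 0.80 |
| 23/16 (47 randomised) | 0.689 / 0.703 | 0.753 / 0.767 | 0.71 / 0.74 |

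With the same SD and method, the drop from 25/21 to 23/16 is 6.5 to 7.5 points.

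**6. If 28 is the number to be analysed**, which is how the sentence reads, the number to randomise is 28 / 0.90 = 31.1, so 32, plus 28 / 0.75 = 37.3, so 38: 70 in all. Taking 28/28 as giving exactly 80%, 23/16 gives about 65%.

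**7. The stated detectable differences.** A difference equal to the SD needs 2 × (1.645 + 0.842)² = 12.37, so 13 per arm. At 28/28 it would have 98% power, not 80%.

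**The case against.** The strongest objection is that the only differences the plan calls detectable are 2.822 and 2.588 units. If those are meant, 23/16 completers give about 92% power (87% to 88% for a difference of 2.588 with SD 2.822), and nothing is lost. The arithmetic is right, but this reading needs 13 per arm and so contradicts the plan's own 28. It shows that the section must state the difference entered. It does not rescue the 80%. What stands is that d = 2 is an inference, and the 73% depends on it.

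Other points on that side:

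- *The 70-patient reading is unlikely.* Agreed: both 28s reproduce as already inflated. It matters only if the sponsor confirms that 28 means completers.
- *The timing of losses is not given.* Tests fall at baseline, after the programme and 3 months later. If some losses come after the second assessment, power there lies between the 23/16 figures (69% to 77%) and the 26/21 figures with no loss (77% to 84%).
- *The Design section says a minimum of 47.* That permits more patients but does not plan for them; section 2.e gives 47 as the need.
- *Mixed models can use partly observed patients.* True, but the 80% comes from a comparison of two means, and the plan offers no calculation based on a mixed model.
- *Rounding 25.2 up to 26 is trivial, and 26:21 follows from the same subtraction.* Both are fair. They need tidying but add nothing to the size of the problem.

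**Conclusion.** The concern holds. That losses are subtracted and the remainder randomised can be read directly from the text and needs no assumption. Its size does: with a difference of 2 units at one-sided 0.05 and the plan's own loss rates, power is about 73% (69% to 77%) against 80% stated. Randomising 28/28 would give about 79% to 80% (76% to 83%). The shortfall is 9 patients (47 against 56), or 23 (47 against 70) if 28 is the number to be analysed.

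These figures show only that the plan misses its own number. Its SDs are spreads of two or three group means over time, not spreads between patients, and PANSS is listed as a secondary variable. They say nothing reliable about power for memory or executive function. The planned rank tests are not covered by the t and normal range.

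**What to change.** Make section 2.e, the Design section and the Workplan agree, in one of two ways:

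- **Keep 47.** State about 23/16 expected completers and one-sided power of about 73% (69% to 77%) in place of 80%. This changes wording only.
- **Randomise 28/28 (56).** State about 25/21 expected completers and power of about 79% to 80% (76% to 83%). This costs nine more patients.

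In either case:

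- Say what the bracketed 2 is, and replace the 2,822 and 2,588 units with the difference actually entered. If it was not 2, redo the power figures.
- Say whether 28 is the number randomised or the number analysed. If it is the number analysed, the total to randomise is 70.
- Make the stated allocation ratio match the group sizes, and correct the 28 − 2.8 step.
- Note beside the power figure that it rests on SDs computed from group means of PANSS negative symptoms and does not apply to memory or executive function.
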